### 2.3.1. Efficacy

Myo-inositolhexaphosphate prevents vascular calcification in non-uremic and uremic animal models. Published studies [16, 17, 44], as well as the non-clinical studies with SNF472 have shown that parenteral IP6 significantly prevents vascular calcification by between 60% and 95% in animal models. The SNF472 efficacy data obtained in animals have helped characterise the concentration-effect relationship and were used to predict potential doses for human clinical

studies. The maximum therapeutic effect was observed at either a dose of 1 mg/kg in rats in the vitamin D model or plasma levels in the 5000-10000 ng/mL (7.5-15 µM) range, depending on the specific model used.

In animal models of calciphylaxis, where a dystrophic calcification in rat's soft tissues is induced, IP6 clearly reduces plaque formation (calcinosis cutis) induced by KMnO4. Calcification was significantly lower in animals receiving IP6. In rats sacrificed two days after KMnO4 treatment calcified deposits were only found in injured tissues of non-IP6 treated groups (Study No EF2004\_10 [45, 46]).

IP6 has also been shown to inhibit mineralisation in vitro of MC3T3 –E1 osteoblasts cultures [28]. The potential mechanism is through binding to growing HAP crystals and by induction of osteopontin expression. When human mesenchymal stem cells (pre-osteoblasts) were incubated with IP6, bone formation activity was enhanced [29].

#### **SNFCT2012\_03 Pharmacodynamic Data:**

Pharmacodynamic assessments (calcification potential of plasma [47]), in healthy volunteers showed a 80% inhibition at 5 mg/kg SNF472, which appeared to plateau thereafter since the effects were the same for the 9 and 12.5 mg/kg doses.

#### **SNFCT2012\_03 Pharmacodynamic Data:**

Pharmacodynamic assessments in haemodialysis patients showed an 80% inhibition at 9 mg/kg SNF472.

#### **SNFCT2014\_03 Pharmacodynamic Data:**

Pharmacodynamic assessments in haemodialysis patients showed an 80% inhibition from 5 mg/kg SNF472 onwards. Less than 20% effect was seen at 1 mg/kg.

### **2.3.2. Safety**

SNF472 was studied in rats and dogs in different toxicology and safety studies, which range from 28 days up to 3 months of treatment.

In the 28-day studies in rats high concentrations produced local irritation. In the 13-week studies, 15-minute daily intravenous administration of SNF472 in rats and dogs induced no mortality and there were no findings attributable to a direct systemic effect of SNF472.

The cardiovascular and respiratory safety pharmacology was assessed in anaesthetised rats and conscious dogs (28-day toxicology and telemetry). In rats, SNF472 did not show any clinically relevant effects on heart rate or blood pressure. In rats and dogs, no effects on respiratory parameters were observed. In dogs, the ECG was evaluated in a 28-day IV (~6-minute bolus) and in a GLP telemetry study. There was a slight heart rate increase in males and females only at the highest dose (30 mg/kg; Cmax: 359432 ng/mL). These effects appear to be Cmax-related. In the telemetry

study SNF472 was administered as long infusion periods (2 hours) and short infusion times (6-minute bolus). Plasma SNF472, calcium, and potassium levels were evaluated. Health status, body weight, cardio-respiratory function, ECG, body temperature, total (serum), and free (blood) concentrations of potassium were not affected by a 2-hour infusion of SNF472 at 3 mg/kg, 10 mg/kg, or 30 mg/kg. QTc prolongation was observed with the 6-minute bolus at 30 mg/kg, but no QTc prolongation was seen with the 2-hour infusion at any of the doses. During the 2-hour infusion, plasma concentrations achieved similar  $C_{max}$  values (318180 ng/mL) as with a bolus (although this might be an under-estimation as it is difficult to pinpoint  $C_{max}$  after a bolus injection).

Please refer to the Investigators Brochure [26] for further toxicology data.

### **SNFCT2012\_03 Healthy Volunteers Safety data**

There were no SAEs, no deaths, and no withdrawals due to AEs during the study. The number of subjects with TEAEs (Treatment emergent adverse event) was similar for all dose groups. TEAEs were mostly mild in intensity and 3 episodes of moderate intensity were reported for the 5.0 mg/kg SNF472 dose and 4 episodes for the 12.5 mg/kg dose.

No clinically significant changes were observed in plasma calcium levels. Although ionised calcium levels were measured, several errors occurred in terms of sampling and analysis:

- As a result of incorrect handling and extraction of samples, the majority of the samples could not be analysed.
- Due to analytical errors, several results in the samples analysed were considered invalid.

The most complete data from ionised calcium set was obtained for the 5 mg/kg dose. In the 12.5 mg/kg dose, there appeared to be a decrease in ionised calcium within the normal range. The baseline values for the other doses were limited. No formal statistical analysis could be done due to the sparse data. In an attempt to get an idea of baseline values in the study populations, we used the ionised calcium before the infusion of placebo or active drug was started, as well as the 12-hour values (8 hours after  $C_{max}$  at a time when no SNF472 was detectable in the blood) and we compared with values obtained around  $t_{max}$  and per dose. Hence, the ionised calcium concentrations seem to be similar to the pooled baseline values with 5 mg/kg of SNF472. With the 9 mg/kg dose, the two available values seem to be at the lower end of the distribution of baseline values, whereas with 12.5 mg/kg dose, two of the three available values are below the baseline values. The data, although sparse, suggest that there possibly was a dose-related decrease in ionised calcium.

There were, however, no clinical features of hypocalcaemia or clinically relevant increases in QTc observed with any of the three doses evaluated. SNF472 concentrations achieved with 12.5 mg/kg were around eight-fold higher than the anticipated therapeutic concentrations.

[figure not shown]

Figure 1 Ionised calcium concentration at the time of peak concentrations with each dose compared to baseline.

Baseline values are a (placebo pre-dose and at 12 hours, b (active treatment pre-dose) and c (active treatment at 12 hours). (mmol/L). Green line: Normal range:1.17-1.30 mmol/L. Red line: 0.5 mmol/L: possibility of tetany and potentially life-threatening

The planned doses in the protocol were 0.5, 1.5, 5, and 10 mg/kg. PK simulation based on preclinical data predicted plasma concentrations ( $C_{max}$ ; ng/mL) of 3000, 10000, 30000 and 70000 respectively. After the 1st cohort (0.5 mg/kg), the DESC (Dose Escalation Safety Committee) decided to increase the dose to be tested in the 2nd cohort (1.5 mg/kg) to 5 mg/kg. This decision was based on PK results showing much lower values than the anticipated systemic exposure of around 2500 ng/mL as predicted by the PK model (levels were below the limit of quantification of 500 ng/mL). According to new PK estimations, 5 mg/kg was expected to produce the initially expected level of exposure with 1.5 mg/kg. The  $C_{max}$  with 5 mg/kg was 11571 ng/ml, which is nearly triple the anticipated EC50. Using the PK data of the 5 mg/kg dose and the safety data after each cohort, the DESC decided to modify the following two doses to reach the target concentrations. The doses of 9 and 12.5 mg/kg produced SNF472 plasma levels of 24394 and 42207 ng/mL, respectively.

### **SNFCT2012\_03 and SNFCT2014\_03 Haemodialysis Patients. Safety data**

The single dose study in haemodialysis patients (SNFCT2012\_03) and up to 28-day MAD study in haemodialysis patients (SNFCT2014\_03). Both have been finalised. The dose range explored in these 2 studies was between 1 mg and 20 mg/kg, and in the MAD 10 mg/kg was administered 3 times a week for one month. Although unblinded, the data are still being analysed, the PK results suggest dose-linearity, no accumulation, and an exposure at 20 mg/kg in the range of 68000 ng/mL. Expected therapeutic levels are around 5000 ng/mL. The preclinical safety margin is

established in 127291 ng/mL. No significant safety and tolerability issues were reported. One single SAE was observed, not related with the drug.

As a conclusion for Phase 1 clinical trials performed with SNF472 up to date: treatment-emergent adverse events seen exclusively in healthy volunteers and not in HD patients, and assessed as probably related to the investigational medicinal product (IMP), were infusion site pain, infusion site erythema, infusion site hypoesthesia, and infusion site swelling. Treatment-emergent adverse events, assessed as possibly related to the IMP, were injection site bruising, headache, dizziness, pain in extremity, eyelid injury, and myalgia. These effects were not seen in HD patients. A single SAE was recorded and was not related to treatment. No clinical significant effects were observed on vital signs, or in the laboratory tests. ECGs, including the QTc interval, was fully evaluated and no clinically significant effects were observed. It showed the following:

- QTcB prolongation in HV was found (all values were below 450 msec). Sparse ionised calcium data suggested mild hypocalcaemia, correlating with QTcB
- QTcB prolongation in HD patients occurred with active as well as placebo treatment. It was not associated with hypocalcaemia and a relationship to chelation of calcium can be ruled out

QTc changes are often seen in HD patients and can be due to the composition of the dialysis fluid, underlying cardiovascular disease, changes in Ca, Mg, or K, or due to medication. As HD patients showed no significant decreases in ionized Ca, SNF472 does not affect hERG channels and QTcB prolongations also occurred in placebos; an SNF-related effect is therefore highly unlikely.

### **2.3.3. Galenics**

SNF472 administered i.v. is 100% bioavailable. No compliance issues will be expected with the IV route in patients who undergo regular dialysis.

### 3. STUDY OBJECTIVES

This is an open label, single arm clinical trial to investigate the effect of SNF472 in uraemic calciphylaxis patients, on top of standard of care. The study objective is to evaluate the effect of SNF472 on top of standard of care on promoting wound healing and other parameters of therapeutic response in haemodialysis patients with CUA. "Standard of care" of calciphylaxis is not defined by evidence or guidelines. However, experts in the field suggest a personalised management plan for each patient based on a list of potential measures which have recently been summarized [39, 41].

## 4. OVERALL DESIGN AND PLAN OF THE STUDY

### 4.1. Overview

[REDACTED] To reach the study objectives, 15 evaluable CUA patients who complete the 12-week treatment period will be enrolled

[REDACTED] will be responsible for the diagnosis of CUA together with the locally treating physician at the study site (team decision, two-pairs-of-eyes decision). The decision to include the patient into the study should be made based on the following criteria [48]:

- The diagnosis of calciphylaxis can be made when:
  1. The following clinical features are all present, or
  2. Two of the following clinical features and typical histopathological findings are present
- Clinical features:
  1. A patient on chronic haemodialysis or haemofiltration or haemodiafiltration for chronic kidney disease
  2. More than 2 painful and non-treatable skin ulcers with concomitant painful purpura
  3. Painful and non-treatable skin ulcers on the trunk, extremities, or penis with concomitant painful purpura
- Histopathological findings:

Skin biopsy is recommended only if the three clinical findings presented above are not present and will be left to the discretion of the treating physician. Typical histopathological findings of the skin are as follows:

  - Necrosis and ulceration of the skin with calcification of the tunica media and internal elastic membrane of small to medium-sized arterioles of dermis and subcutaneous fat
  - Concentric stenosis due to oedematous intimal thickening of the small to medium-sized arterioles of dermis and subcutaneous fat

Intense pain as primary manifestation followed and associated with cutaneous lesions and palpation of firm calcified (leather-like) subcutaneous tissue surrounding the lesion is suggestive of calciphylaxis. Typically, the lesions do not occur at sites primarily affected by venous insufficiency or arterial malperfusion. In view of the painful character of the lesions, palpation is left to the discretion of the treating physician.

The diagnosis of calciphylaxis can be supported by findings obtained from a skin biopsy. Benefits of a biopsy include exclusion of other conditions that can mimic calciphylaxis such as vasculitis. The characteristic histological features of calciphylaxis include calcification, microthrombosis, and fibrointimal hyperplasia of small dermal and subcutaneous

arteries and arterioles, leading to cutaneous ischemia and intense septal panniculitis. Von Kossa or Alizarin red staining are required to detect micro calcification. [REDACTED]  
[39-41].

Performing a skin biopsy will be left to the discretion of the treating physician and will be performed following the site's SOPs. In case the biopsy is performed as a routine procedure at the site, and the result is positive for CUA, the patient is included – as long as the “gatekeeper”, [REDACTED] agrees with the remaining diagnostic parameters. If the biopsy is negative, [REDACTED] will check the biopsy results and will decide if he agrees or disagrees with the remaining diagnostic parameters to include or not the patient.

In order to have readable biopsies, the following requisites need to be fulfilled:

1. site of biopsy: the biopsy should include the ulcer borders, not the necrotic core, and be deep enough to show deep skin layers
2. the biopsy material should be fixed in either formalin or paraformaldehyde or glutaraldehyde
3. paraffin blocks should be mailed to the core pathology lab [REDACTED] where appropriate stains such as EVG, von Kossa, etc. will be performed

Wound treatment of calciphylaxis ulcerations will be performed according to local good clinical practice SOPs of the corresponding clinical site irrespective of the fact that the ulceration might be evaluated as treatment target within the trial. Such a wound treatment SOP might include the interdisciplinary team approach by nephrologists, dermatologists, (plastic) surgeons, and specialized nurses.

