#### 5.4. Exclusion Criteria

Patients who meet one or more of the following criteria will not be considered eligible to participate in the clinical trial:

1. Body weight above 150 kg
2. BMI >35 and central(abdominal) ulcers
3. History of bisphosphonate treatment within 12 months before entering into the study
4. Severely ill patients without reasonable expectation of survival for > 6 months according to the treating physician
5. Patients with scheduled parathyroidectomy during the run-in or study period
6. Female patients who are either intending to get pregnant or are undergoing treatment to get pregnant, as well as breast-feeding females
7. Participation in another clinical trial with an experimental drug within 90 days prior the inclusion
8. Any psychological, emotional problems, any disorders or resultant therapy that is likely to invalidate informed consent, or limit the ability of the patient to comply with the Clinical Trial Protocol requirements
9. Patients who, in the opinion of the Investigator, are considered unsuitable for any other reason

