### 7.1.2.2. Definitions

An adverse event (AE) is any unfavourable and unintended sign, symptom, or disease that appears or worsens in a subject or clinical investigation subject during the period of observation in a clinical study.

The adverse event may be any of the following:

- A new illness,
- An exacerbation of a sign or symptom of the underlying condition under treatment or of a concomitant illness (including abnormal laboratory finding)
- Unrelated to participation in the clinical study or an effect of the study medication or comparator drug, or
- A combination of one or more of the above factors.

No causal relationship with the study medication is implied by the use of the term “adverse event.” An exacerbation of a pre-existing condition/illness is defined as a more frequent occurrence or as an increase in the severity of the pre-existing condition/illness during the study. Planned or elective surgical or invasive procedures for pre-existing conditions that have not worsened are not adverse events. However, any complication that occurs during a planned or elective surgery is an adverse event. (If the event fits the seriousness criteria, such as an extended hospitalisation, it will be considered a serious adverse event.) Conditions leading to unplanned surgical procedures may be adverse events.

In order for the Sponsor to collect additional information about the clinically important laboratory or diagnostic tests (eg, blood, urinalysis, ECG, imaging) abnormalities, at a minimum, the following abnormalities should be captured on the AE CRF:

- Any test result that meets the criteria for a SAE
- Any test abnormality that suggests a disease and/or organ toxicity that is new or has significantly worsened
- Any test abnormality that required the subject to have study medication discontinued or interrupted

- Any test abnormality that required the subject to receive specific corrective therapy, close observation, more frequent follow-up assessment, or further diagnostic investigation

Laboratory test abnormalities may not be of clinical significance in the absence of:

- Clinical symptoms
- Change in lifestyle
- Need for intervention

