9.2 Efficacy Analysis

9.2.1 Primary endpoint

The primary endpoint is the absolute change in BWAT total score between baseline (Week 1) and Week 12 for the primary lesion (the largest one).

Absolute change from baseline will be calculated as differences in the total score from Week 1 to Week 12. Descriptive statistics will be presented. Differences between the two visits will be analyzed using a Paired Student's T-Test. (Shell T-7)

Missing imputation will be done on the item level. For the imputation of baseline missing item scores FOCB will be used for LOCF imputation method if any subsequence item score is available, else the score will be imputed by 3. For the multiple imputation method the baseline values will be imputed by 3. The main analysis will be done using Multiple Imputation, and supported by the different sensitivity analysis as specified in Section 8.4. A forest plot summarizing these results will be produced presenting the estimated change from Week 1 to Week 12 and its 95% confidence interval for the different imputation methods (Shell F - 1).

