9.2.2.5 Potential Wound Complications

Sponsor will review all AEs to identify potential wound complications (eg., wound infections, systemic infections, wound complications, surgical treatments of the wound).

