9.7 Subgroup analysis

Subgroup analysis will be summarized for the ITT analysis set. Subgroups will be based on baseline and demographic categories including age (e.g., < 65 years of age and \geq 65 years of age), gender, race, and country, and use of STS (sodium thiosulfate).

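### Wound surgery is a secondary endpoint but is sought only among adverse events, which can omit elective procedures on a study lesion that has not worsened; the STS subgroup also lacks a time reference

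*Protocol*

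**What the plan says.** SAP 5.2.2 lists, among wound and disease complications, whether the wound was treated surgically after baseline. Protocol 4.2.2 lists the same event as a secondary endpoint. Protocol 4.1 leaves wound care to each site's own procedures "irrespective of the fact that the ulceration might be evaluated as treatment target within the trial", and says these might include an "interdisciplinary team approach by nephrologists, dermatologists, (plastic) surgeons, and specialized nurses". Surgery on the primary lesion is therefore foreseen.

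On how such events are found, SAP 9.2.2.5 is a single sentence: "Sponsor will review all AEs to identify potential wound complications". Surgery on the wound is one of its examples. Protocol 7.1.2.2 limits what enters that source: "Planned or elective surgical or invasive procedures for pre-existing conditions that have not worsened are not adverse events".

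For the primary endpoint, SAP 9.2.1 takes the primary lesion's BWAT total at Week 1 and Week 12: "Differences between the two visits will be analyzed using a Paired Student's T-Test". It does not mention procedures between the two visits.

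SAP 8.3, 9.7 and 9.7.2 add subgroup summaries by STS for BWAT and VAS, and a VAS responder table for the STS subgroup. None says whether STS status is fixed at Day 1 or covers any use on study.

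**The concern.** The endpoint covers all wound surgery after baseline, but the source searched for it excludes one class of surgery by definition. Every primary lesion exists at baseline, so it is a pre-existing condition in the protocol's sense. A planned debridement or graft of such a lesion, if it has not worsened, need not be an adverse event.

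Two things are at stake. First, the endpoint can be undercounted, and selectively: the procedures that drop out are those on lesions that have not worsened. Second, someone reading the primary result would not know how many Week 12 scores were taken after an operation on the scored lesion. That matters because two of the 13 scored BWAT items (necrotic tissue type and amount, Protocol 7.5.2) can change when dead tissue is removed, without healing.

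The STS point is similar but smaller. If the subgroup means any use on study, it can combine patients on STS before the first dose with patients given STS later because the lesion was failing. In the second group the response to the outcome helps to define the subgroup.

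**Working it through.** **Which procedures can the adverse event review find?** Reading Protocol 7.1.2.2 with SAP 9.2.2.5:

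- Planned or elective surgery, lesion not worsened, no complication: not an adverse event, so not found.
- Planned or elective surgery with a complication: the complication is an adverse event, so the surgery may be found through it.
- Surgery on a lesion that has worsened: the worsening is an adverse event, and Protocol 7.1.2.4 asks each report to state the treatment required, so the surgery can be found.
- Unplanned surgery: the protocol says only that the condition behind it may be an adverse event, so finding it is likely but not assured.

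**Does another stated route close the first case?**

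- Hospitalisation: SAP 9.2.3 takes hospitalisations from the seriousness field of adverse events, and Protocol 7.1.2.3.1 excludes planned admissions for elective procedures. It does not.
- Concomitant medication (Protocol 6.8.1): covers medicinal products, not procedures.
- Schedule of assessments (Protocol Table 1, SAP 6.2): has no row for wound procedures on study.

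**Size of the undercount.** The plan gives no figure to reproduce and no surgery rate. With N = 15 and k patients whose only wound surgery is of the missed kind (assumed, k = 1 to 5), the reported proportion is too low by k/15:

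- k = 1: 1/15 = 6.7 percentage points
- k = 3: 3/15 = 20.0
- k = 5: 5/15 = 33.3

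**Why the count belongs beside the primary result.** Each BWAT item runs from 1 to 5, so the two necrosis items can fall by at most 2 × 4 = 8 points of the 65 − 13 = 52 available. If k of 15 patients had that full fall from surgery alone, the mean change would shift by 8k/15: 0.53 points for k = 1, 1.6 for k = 3, 2.67 for k = 5. These are ceilings. They need both items to go from 5 to 1 and nothing else to move, and size or depth may rise after surgery.

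A simulated paired t-test (n = 15, no drug effect, normal changes, assumed SD 6 to 10 because the documents give none) shows the chance of a significant improvement, nominally 2.5%:

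| Patients affected | Fall of 4 points | Fall of 8 points |
|---|---|---|
| 3 | 4.3% to 6.1% | 7.2% to 10.4% |
| 5 | 6.5% to 10.5% | 13.0% to 23.5% |

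These figures do not show that bias is present. They show that the number of operated primary lesions is worth knowing when the result is read.

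**STS.** SAP 8.3 names certain medications as a basis for subgroups, apart from its baseline and demographic categories. SAP 9.7 lists STS use at the end of a sentence that opens with those categories. One can be read as any use and the other as use at baseline. Medication changes are recorded (Protocol 6.8.1), so either definition could be programmed, but they give different groups.

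**The case against.** The best defence is that the plan is open about its design. The objective is SNF472 on top of standard of care. Protocol 3 and 4.3 say that standard of care is undefined and personalised, and 4.3 gives the reason for having no control arm. Protocol 4.1 expressly decides that local wound care continues on the target lesion. In a study that the SAP calls exploratory and proof of concept, keeping each score whatever else was done is a coherent choice.

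Other text also helps. Component scores by visit (SAP 9.2.2.1) would show a fall confined to the necrosis items. The image review that compares Week 1 with Week 12 without knowledge of visit order (SAP 6.6.2) gives a second reading of healing. The adverse event exclusion is narrow, and the CRF, which is not among the documents reviewed, may already hold a procedure field. SAP 9.7 can be read as taking STS at baseline.

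Most of this stands, and it answers a broader complaint that a reader might infer: that the plan wrongly credits surgery or new therapy to SNF472. Difficulty in separating the drug from background care follows from the declared single-arm design, and the component scores and blinded images partly expose it. It does not answer the narrower point. SAP 9.2.2.5 names adverse event review and no other source, and a CRF field would not help unless the SAP used it.

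**Conclusion.** The point holds in its narrow form. Followed as written, the plan can undercount a stated secondary endpoint by missing elective procedures on study lesions that have not worsened. The documents do not show how many that would be. Each missed patient costs 6.7 percentage points if N is 15. This rests on SAP 9.2.2.5 being the whole ascertainment rule; the CRF, and any SAP text between sections 8.4 and 8.6, could not be checked. The missing time reference for STS is a smaller, real ambiguity. Both should be corrected, and neither undermines the trial.

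Three stronger readings are not supported:

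- That all wound surgery would be missed. Surgery linked to worsening or to a complication can still surface.
- That the primary result is biased by 8 points, or in a known direction. That figure is a ceiling for one patient on assumed inputs, and the bias could go either way.
- That excluding recent bisphosphonate use at entry, with no rule afterwards, is a contradiction. An entry criterion that looks back does not conflict with silence about later use.

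**What to change.** 1. In SAP 9.2.2.5, take wound surgery from a record of every post-baseline procedure on a study lesion (lesion, type, date), whether or not it is an adverse event. Use the CRF if it has the field, otherwise source documents. Keep the adverse event review for infections and other complications.
2. In SAP 9.2.1, report beside the primary result the number of patients whose primary lesion had surgery before Week 12. The primary analysis itself does not change.
3. In SAP 8.3 and 9.7, define the STS subgroup by recorded start date: ongoing at Day 1 or not. Describe patients who start STS after Day 1 separately, without making them a subgroup.

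The cost is SAP wording and one CRF line (or one retrieval from source) per procedure. STS start dates should already be in the medication record. Subgroup cells will be small, and the two-subject minimum in SAP 8.3 may apply.

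A sensitivity analysis that sets BWAT scores after surgery or new therapy to missing and imputes them is optional. The imputation model in SAP 8.4 uses only endpoint values and other items of the same scale. Patients whose lesions were failing would be filled in largely from patients who needed no added treatment, which may favour SNF472. If the analysis is run, the missing-at-random assumption and that possible direction should be stated with it.
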